HV	healthy volunteer
Hx/Su	Hypoxia/Sugen
i.t.	intra-tracheal
i.v.	Intravenous
ICH	International Conference on Harmonization of Technical Requirements for Registration of Pharmaceuticals for Human Use
IEC	Independent Ethics Committee
IPR	prostacyclin receptor
IRB	Institutional Review Board
IRT	Interactive Response Technology
LDH	lactate dehydrogenase
LLOQ	lower limit of quantification
LV	left ventricular
MAD	multiple ascending dose
MCT	Monocrotaline
mg	milligram(s)
ml	milliliter(s)
mPAP	mean pulmonary artery pressure
MTD	maximum tolerated dose
NOAEL	no observed adverse effect level
NT-proBNP	N-terminal prohormone of brain natriuretic peptide
NYHA	New York Heart Association
PA	pulmonary artery
PAH	pulmonary arterial hypertension
PCWP	Pulmonary Capillary Wedge Pressure
PD	pharmacodynamic(s)
PG	Pharmacogenetics
PH	pulmonary hypertension
PK	pharmacokinetic(s)

PVR	pulmonary vascular resistance
RA	right atrium
REB	Research Ethics Board
RHC	right heart catheterization
RV	right ventricular
SAD	single ascending dose
SAE	serious adverse event
SAP	Statistical Analysis Plan
SD	standard deviation
SOM	Site Operations Manual
SVR	systemic vascular resistance
TBL	total bilirubin
ULN	upper limit of normal
WHO	World Health Organization

Pharmacokinetic definitions and symbols

AUC _{0-t}	The area under the plasma (or serum or blood) concentration-time curve from time zero to time 't' where t is a defined time point after administration [mass x time / volume]
AUC _{last}	The area under the plasma (or serum or blood) concentration-time curve from time zero to the time of the last quantifiable concentration [mass x time / volume]
AUC _{tau}	The area under the plasma (or serum or blood) concentration-time curve from time zero to the end of the dosing interval tau [mass x time / volume]
AUC _{tau,ss}	The area under the plasma (or serum or blood) concentration-time curve from time zero to the end of the dosing interval tau at steady state [mass x time / volume]
C _{av,ss}	The average steady state plasma (or serum or blood) concentration during multiple dosing
CL	The systemic (or total body) clearance from plasma (or serum or blood) following intravenous administration [volume / time]
CL/F	The apparent systemic (or total body) clearance from plasma (or serum or blood) following extravascular administration [volume / time]
CL _r	The renal clearance from plasma (or serum or blood) [volume / time]
C _{max}	The observed maximum plasma (or serum or blood) concentration following drug administration [mass / volume]
C _{max,ss}	The observed maximum plasma (or serum or blood) concentration following drug administration at steady state [mass / volume]
C _{min,ss}	The lowest plasma (or serum or blood) concentration observed during a dosing interval at steady state [mass / volume]
F	Bioavailability of a compound. F _{abs} is the absolute bioavailability, i.e. the fraction (or percentage) of the administered extravascular dose systemically available. F _{rel} is the relative bioavailability, i.e. the bioavailability relative to a reference
T _{1/2}	The terminal elimination half-life [time]
T _{1/2,acc}	The effective half-life based on drug accumulation at steady state [time]
T _{max}	The time to reach the maximum concentration after drug administration [time]
V _{ss}	The volume of distribution at steady state following intravenous administration [volume]

V_z	The volume of distribution during the terminal elimination phase following intravenous administration [volume]
V_z/F	The apparent volume of distribution during the terminal elimination phase following extravascular administration [volume]

Glossary of terms

Control drug	A study drug used as a comparator to reduce assessment bias, preserve blinding of investigational drug, assess internal study validity, and/or evaluate comparative effects of the investigational drug.
Enrollment	Point/time of subject entry into the study; the point at which informed consent must be obtained (i.e. prior to starting any of the procedures described in the protocol).
Investigational drug	The study drug whose properties are being tested in the study; this definition is consistent with US CFR 21 Section 312.3 and is synonymous with “investigational new drug” or “investigational medicinal product”.
Investigational treatment	All investigational drug(s) whose properties are being tested in the study as well as their associated treatment controls. This includes any placebos, any active controls, as well as approved drugs used outside of their indication/approved dosage or tested in a fixed combination. Investigational treatment generally does not include other treatments administered as concomitant background therapy required or allowed by the protocol when used within approved indication/dosage.
Medication number	A unique identifier on the label of each study drug package in studies that dispense study drug using an IRT system.
Period	A minor subdivision of the study timeline; divides phases into smaller functional segments such as screening, baseline, titration, washout, etc.
Premature subject withdrawal	Point/time when the subject exits from the study prior to the planned completion of all study drug administration and assessments; at this time all study drug administration is discontinued and no further assessments are planned.
Randomization number	A unique identifier assigned to each randomized subject, corresponding to a specific treatment arm assignment
Stage	A major subdivision of the study timeline; begins and ends with major study milestones such as enrollment, randomization, completion of treatment, etc.
Study completion	Point/time at which the subject came in for a final evaluation visit or when study drug was discontinued whichever is later.
Study drug discontinuation	Point/time when subject permanently stops taking study drug for any reason; may or may not also be the point/time of premature subject withdrawal.
Study drug/treatment	Any drug (or combination of drugs) administered to the subject as part of the required study procedures; includes investigational drug, active drug run-ins or background therapy.

Subject	An individual who has consented to participate in this study. The term Subject may be used to describe either a healthy volunteer or a patient.
Subject number	A number assigned to each subject who enrolls in the study. When combined with the center number, a unique identifier is created for each subject in the study.
Variable	Information used in the data analysis; derived directly or indirectly from data collected using specified assessments at specified timepoints.

Corporate Confidential Information

Corporate Confidential Information

Corporate Confidential Information

Protocol synopsis

Protocol number	[CQCC374X2201]
Title	A randomized, parallel-group, placebo-controlled subject and investigator blinded study to assess the safety, tolerability, pharmacokinetics and efficacy of QCC374 in the treatment of pulmonary arterial hypertension (PAH)
Brief title	Safety, pharmacokinetics and efficacy study of QCC374 in PAH patients
Sponsor and Clinical Phase	Novartis Phase II (non-confirmatory)
Intervention type	Drug
Study type	Interventional
Purpose and rationale	This study is designed as a proof of concept study for QCC374, an inhaled prostacyclin receptor (IPR) agonist for the treatment of PAH. The purpose of this study is to assess the safety, tolerability, pharmacokinetics and efficacy of QCC374 in adult patients with PAH to determine if QCC374 has an adequate clinical profile to warrant further clinical development in this indication.
Primary Objective(s)	To assess the efficacy of 16 weeks of QCC374 administration in patients with PAH by measuring the change from baseline in pulmonary vascular resistance (PVR).
Secondary Objectives	
 • To evaluate the safety and tolerability of multiple doses of QCC374 in patients with PAH • To evaluate the preliminary efficacy of 16 weeks of QCC374 administration in patients with PAH by measuring changes from baseline in: 
 • Six minute walk distance (6MWD) • Hemodynamic parameters other than PVR • Right ventricular function with echocardiography • To evaluate the pharmacokinetics of QCC374 and its metabolite QCM441 in patients with PAH
Study design	
This is a non-confirmatory, randomized, subject and investigator blinded, placebo controlled study of QCC374 in PAH patients. The study will have 2 parts. In Part 1, an initial safety cohort, 8 subjects will be randomized in a 6:2 ratio and the starting dose will be 0.03 mg bid. In Part 2, ~ 30 subjects will be randomized in a 2:1 ratio, with a starting dose of 0.03 mg bid. In Part 1, subjects will be up-titrated during the first two weeks of the study to 0.12 mg bid, or to their maximum tolerated dose (MTD) if their individual MTD is below 0.12 mg bid during the first two weeks of the study.
 
In Part 2, subjects will be up-titrated during the first two weeks of the study to 0.06 mg bid, or will remain at the starting dose of 0.03 mg bid if the investigator believes, based on their medical judgement, that the dose should not be increased.
 
The treatment duration is 16 weeks.

Population	The study population for Parts 1 and 2 will be comprised of male and female adults with symptomatic PAH. A total of approximately 38 patients are planned to be enrolled and randomized, with approximately 30 patients expected to complete the study. The sample size will be re-estimated at the interim analysis and number of randomized patients may be increased up to a maximum of 60.


Inclusion criteria
	
Male and female patients 18 years of age or older with symptomatic PAH.
 
Subjects with PAH belonging to one of the following subgroups of the Updated Clinical Classification Group 1 (Nice, 2013):
 
 • idiopathic PAH • familial PAH • PAH associated with connective tissue disease, congenital heart disease (surgically repaired at least 12 months prior to screening) or drug or toxin induced (for example, anorexigen use). 
Subjects must have persistent symptoms due to PAH despite therapy with at least one of the following PAH medications: an endothelin receptor antagonist, a soluble guanylate cyclase stimulator or a phosphodiesterase inhibitor. The subjects' PAH medication regimen, with typical medications including endothelin receptor antagonists, soluble guanylate cyclase stimulators and/or phosphodiesterase inhibitors, must have been used at a stable dose and frequency for at least 12 weeks before the screening visit and during the screening period.
 
Diagnosis of PAH established according to the standard criteria before the screening visit:
 
 • Resting mean pulmonary arterial pressure (mPAP) \geq 25 mmHg • PVR $>$ 240 dyn·s/cm⁵ • Pulmonary capillary wedge pressure (PCWP) or left ventricular end diastolic pressure \leq 15 mmHg 
PVR $>$ 400 dyn·s/cm⁵ at the time of the baseline right heart catheterization (RHC) (if a RHC was completed within one month of the screening visit, that result may be used for inclusion, if data meets criteria outlined in Section 8.5.1).
 
6MWD greater than 150 meters at screening. This distance must be confirmed by a second 6MWT prior to randomization. The value of the second 6MWD should be within \pm 15% of the value obtained at screening.


Exclusion criteria
	
Subjects with clinically unstable right heart failure within the last three months (New York Heart Association (NYHA) Class IV).
 
Subjects with PAH associated with portal hypertension, Human Immunodeficiency Virus (HIV) infection or unrepaired congenital systemic to pulmonary shunts
 
Subjects who have received or have been scheduled to receive long-term treatment with epoprostenol or any prostacyclin within the three months prior to the screening visit or during the screening period.
 
Hypotensive subjects (systemic systolic blood pressure $<$ 85 mmHg)
 
Subjects with three or more of the following left ventricular disease/dysfunction risk factors: Body mass index (BMI) $>$ 30 kg/m² at the screening visit (BMI = Body weight (kg) / [Height (m)]²); History of Essential Hypertension; Diabetes Mellitus – any type; Medical history of significant coronary artery disease (CAD).
 
Subjects with left sided heart disease, chronic left sided heart failure, congenital or acquired valvular disease and/or pulmonary venous hypertension.
 
Subjects with obstructive (FEV1/FVC $<$ 70% and FEV1 $<$ 70% predicted) or restrictive (total lung capacity $<$ 65% predicted and/or clinically significant abnormality on CXR) lung disease at screening.

Investigational and reference therapy	
 • QCC374 0.015 mg • QCC374 0.06 mg
Efficacy/PD assessments	
 • PVR • 6MWD • mPAP, PCWP, Cardiac Output (CO), Systemic Vascular Resistance (SVR) • Right Ventricular (RV) function with echocardiography
Safety assessments	
 • Spirometry • Electrocardiogram (ECG) • Chest X-ray (CXR) • Blood Chemistries, Hematology and Urinalysis
Other assessments	
 • Pharmacokinetics (PK) 
Corporate Confidential Information

Data analysis	
Data from the two parts of the study will be pooled for the statistical analysis.
 
The primary variable is PVR. The log transformed PVR is expected to be approximately normally distributed. The change from baseline (on log transformed values) will be analyzed using an Analysis of Covariance (ANCOVA) model with treatment as a factor and log transformed baseline PVR as a covariate. Likelihood based posterior distributions will be derived to assess the probability that QCC374 is better than placebo and the probability that the reduction vs placebo is at least 15%.
 
The efficacy criteria at the end of the study is as follows:
 
 • If there is at least 90% probability that the treatment effect of QCC374 is better than placebo in PVR and • If there is at least 50% probability that the reduction in PVR is at least 15% in favor of QCC374 compared to placebo.
Key words	Pulmonary Arterial Hypertension, Prostacyclin

1 Introduction

1.1 Background

Pulmonary arterial hypertension (PAH) is a progressive disease characterized by chronic elevation of mean pulmonary artery pressure (mPAP) and pulmonary vascular resistance (PVR), defined as a mPAP \geq 25 mmHg at rest, a PVR $>$ 240 dyn.s.cm⁻⁵, and pulmonary capillary wedge pressure (PCWP) \leq 15 mmHg (Galie et al 2015). The Updated Clinical Classification of Pulmonary Hypertension (Simonneau et al 2013) classifies pulmonary hypertension (PH) into five groups, based on similarities in clinical presentation, pathophysiology, prognosis and therapeutic approach. Within this classification, PAH is classified as Group 1 PH. Most cases of Group 1 PAH are idiopathic (i.e., not associated with known risk factors or conditions), but PAH also occurs in a heritable form and in association with other disorders, including collagen vascular diseases, congenital systemic-to-pulmonary shunts, ingestion of drugs/toxins or other systemic conditions such as HIV infection or portal hypertension.

A variety of arterial abnormalities characterize the pathology of PAH, including intimal hyperplasia, medial hypertrophy, adventitial proliferation, thrombosis in situ, varying degrees of inflammation, and plexiform arteriopathy. These remodeling changes are paramount in the pathogenesis of PAH, resulting in loss of luminal cross-section and increased PVR (Schermuly et al 2011), with only $<$ 20% of PAH patients demonstrating a dynamic vasoconstrictive component of their disease (McLaughlin et al 2009). Progressive vascular remodeling and increased PVR results in increased workload for the right ventricle and right ventricular failure, which is the major cause of PAH associated mortality.

Over the last 20 years, significant advances have occurred in the treatment of PAH with the development of marketed therapies targeting three pathways: the endothelin, nitric oxide and prostacyclin pathways. Therapies targeting the prostacyclin pathway include the synthetic prostacyclin epoprostenol, prostacyclin analogs such as iloprost and treprostinil, and the IPR agonist selexipag. Prostacyclins are available via intravenous (epoprostenol, treprostinil), subcutaneous (treprostinil), inhaled (nebulized treprostinil and iloprost) and oral routes (treprostinil, beraprost (Japan only), selexipag). Despite these therapies, however, PAH remains a fatal disease with a median survival from diagnosis of 7 years (Benza et al 2012).

Prostacyclin (Prostaglandin I₂, PGI₂) is primarily produced by endothelial cells, formed from arachidonic acid via the cyclooxygenase pathway. The prostacyclin receptor (IPR) is widely expressed on multiple cell types, including vascular smooth muscle, fibroblasts, endothelium and various inflammatory cells (Woodward et al 2011). The vasodilatory action of prostacyclins is well validated in the clinic, and there is also growing non-clinical evidence that prostacyclins will impact upon the underlying structural changes that lead to increased vascular resistance, reversing the remodeling of pulmonary vessels. Inhaled iloprost has been shown to reverse vascular remodeling in a monocrotaline (MCT) induced PAH model in the rat (Schermuly et al 2005). In addition to normalization of PVR, iloprost reduced right heart hypertrophy and pulmonary vascular thickening. In another study using the MCT model, selexipag was also able to prevent vascular remodeling (Kuвано et al 2008).

Prostacyclins have also been associated with anti-inflammatory (Hayashi et al 2010) and anti-fibrotic effects (Zhu et al 2010).

Prostacyclins (e.g. epoprostenol, treprostinil, iloprost, selexipag) have been associated with improvements in pulmonary hemodynamics in PAH patients both acutely and following short term chronic dosing (e.g., 12-17 weeks) (Barst et al 1996; McLaughlin et al 2010; Simonneau et al 2002; Simonneau et al 2012). These chronic effects are associated with improvement in exercise capacity (e.g., 6MWD) and functional status. In a 12 week open randomized study, epoprostenol was associated with improved survival in naive, severe Functional Class III/IV patients (Barst et al 1996). Most recently, in a time to clinical worsening (Phase 3 study with 1156 PAH patients treated for up to 4.2 years, selexipag decreased the risk of a worsening event versus placebo by 39%. Currently the effect of prostacyclins (and other PAH therapies) on chronic pulmonary vascular remodeling in the clinic is poorly characterized, in part due to the lack of validated endpoints/biomarkers to represent this process.

All prostacyclins have limitations impacting their safety and potential efficacy profile. Parenteral and oral IPR agonists are associated with on-target dose-limiting adverse events, including headache, jaw pain, nausea, diarrhea and hypotension, and require titration to an individual maximum tolerable dose. Nebulized iloprost and treprostinil are also dose limited by systemic adverse effects and have a relatively short duration of action, with both factors likely contributing to modest efficacy of these agents. As a result of these shortcomings, the initiation of prostacyclin therapy is delayed in some PAH patients, with a clear subsequent negative effect on prognosis (Badagliacca et al 2012).

To address these shortcomings, QCC374 has been designed as a chemically stable, selective inhaled IPR agonist for dry powder inhalation, with long duration of action (via optimized cell membrane affinity) and low systemic exposure (high plasma protein binding, rapid clearance). These characteristics are expected to lead to a considerably improved safety and tolerability profile and potentially increased efficacy compared to other members of the prostacyclin class.

Corporate Confidential Information

Corporate Confidential Information

Corporate Confidential Information

1.4 Study purpose

This study is designed as a proof of concept study for QCC374, an inhaled IPR agonist for the treatment of PAH. The purpose of this study is to assess the safety, tolerability, PK and efficacy of QCC374 in adult patients with PAH and determine if QCC374 has an adequate clinical profile to warrant further clinical development in this indication.

2 Study objectives and endpoints

2.1 Primary objective(s)

Primary objective(s)	Endpoints related to primary objective(s)

To assess the efficacy of 16 weeks of QCC374 administration in adult patients with PAH	
Percentage of the baseline PVR at week 16.

2.2 Secondary objective(s)

Secondary objective(s)	Endpoints related to secondary objective(s)

 To evaluate the safety and tolerability of multiple doses of QCC374 in patients with PAH 	
 AEs, SAEs and all safety assessments

 To evaluate the preliminary efficacy of 16 weeks of QCC374 administration in patients with PAH by measuring changes from baseline in: 
 Six minute walk distance (6MWD) Hemodynamic parameters other than PVR Right ventricular (RV) function with echocardiography 	
 6MWD mPAP, PCWP, CO, SVR Key RV function endpoints with echocardiography including but not limited to tricuspid annular peak systolic velocity (TA S'), RV Tei index and RV fractional area change.

 To evaluate the pharmacokinetics of QCC374 and its metabolite QCM441 in patients with PAH 	
 PK parameters of primary interest (C_{max}, T_{max}, AUC_{last}, AUC_{tau}) of QCC374 and QCM441 in plasma.

Corporate Confidential Information

3 Investigational plan

3.1 Study design

This is a non-confirmatory, randomized, subject and investigator blinded, placebo controlled study of QCC374 in PAH patients. The study will have 2 parts: Part 1, an initial safety cohort with a 0.03 mg bid starting dose, and Part 2, a larger cohort with a 0.03 mg bid starting dose. An unblinded review of all available safety data will be reviewed prior to starting Part 2. The treatment duration is 16 weeks for both parts.

Study flow and procedures (common to all parts, [Figure 3-1](#)):

Screening Period (up to 28 days)

During this period eligibility will be confirmed. During the screening phase subjects do not receive any study medication.

Titration Period (2 weeks)

The study dose can be titrated during the initial two week period, as described below for Parts 1 and 2.

Stable Dose Follow-up (14 weeks)

No further adjustments in dose should occur unless a dose reduction for tolerability or safety reasons is indicated. In the event of a dose reduction, the subject could subsequently be increased back to the dose achieved at the end of the Titration Period, but increases above the dose level reached at the end of the Titration Period are not allowed.

Safety Follow-up Period:

For all patients stopping study treatment prematurely at any time of the study or who decide not to participate in the long term extension phase study, a safety follow-up visit 28 days after the stop of study medication intake should be performed.

Figure 3-1 Study Periods

- Screening Period: up to 28 days
- Titration Period: 2 weeks
- Stable Dose Follow-up Period: 14 weeks
- Safety Follow-up Period: 4 weeks*

*only for patients who do not enter the open label extension trial (there will be a separate protocol for QCC374X2201E1 study) or who stop the study medication prematurely

General Notes:

- QCC374 will be administered via inhalation using the Concept1 dry powder inhaler
- At the end of the treatment period of 16 weeks, eligible patients will be given the option to participate in a separate long term extension study, where all patients will be treated with an individual optimal dose of QCC374.
- Patients who complete Visit 108 (Day 111) and do not wish to enroll in the extension study will receive study drug on the morning of Visit 109 (Day 112) and complete PK and indicated safety assessments. These patients will not receive the pm dose of study drug. The last visit for these patients is the End of Study Visit (Visit 202), 28 days after receiving last dose of study drug.

3.1.1 Part 1

[figure not shown]
Part 1 (Figure 3-2) will consist of 8 subjects, randomized in a 6:2 ratio to QCC374 or placebo. The planned bid dose levels in Part 1 are 0.03 mg, 0.06 mg and 0.12 mg. Subjects will begin dosing at 0.03 mg bid.

- On Day 4 the investigator will assess an individual subject's clinical status and reported adverse events and confirm that an individual subject can be up-titrated to 0.06 mg bid. This decision, made individually for every subject, will be based on the investigator's assessment of the severity of any adverse events, including adverse events typical of prostacyclins (e.g. headache, jaw pain, myalgia, flushing and nausea).
- On Day 7 the investigator will assess an individual subject's clinical status and reported adverse events and confirm that an individual subject can be up-titrated to the next planned dose level. This decision, made individually for every subject, will be based on the investigator's assessment of the severity of any adverse events, including adverse events typical of prostacyclins.
- On Day 14 the investigator will assess the patient's clinical status and reported adverse events. If the patient is not already receiving the maximum dose of 0.12 mg bid, the investigator will determine whether an individual subject can be up-titrated one dose level.

This decision, made individually for every subject, will be based on the investigator's assessment of the severity of any adverse events, including adverse events typical of prostacyclins.

- Following the Day 14 visit no further up-titrations are allowed. Subjects are allowed to continue in the trial even if their final dose after titration on Day 14 is not 0.12 mg.
- On Day 21, if the subject's dose was up-titrated on Day 14, a follow-up phone call visit will occur to review safety and tolerability.
- At any point during the 16 week treatment period, if the investigator believes, based on their medical judgement, that the dose should be reduced due to the severity of adverse events, the investigator will reduce the dose to the previous tolerated dose. A follow-up phone call should be scheduled 7 days after dose adjustment to review safety and tolerability of adjustment.

Figure 3-2 Part 1 and Part 2 Dose Evaluation and Titration

= dose evaluation. The investigator will assess an individual subject's clinical status and reported adverse events. The investigator will increase the dose to the next level unless he/she believes, based on their medical judgement, that the dose should not be increased due to the severity of typical pharmacologic effects of IP-receptor agonists (including headache, jaw pain, myalgia, flushing and nausea).

#Part 2 will begin only after a safety evaluation of Part 1, triggered when 8 subjects in Part 1 have completed 2 weeks of dosing. The safety data reviewed will include AE listings, vital signs, spirometry and ECG data. The dosing regimen in Part 2 is subject to change, based on information from Part 1.

*0.12 mg BID is the maximum dose in Part 1, but a subject may continue in the study at a lower dose if 0.12 mg BID is not reached by Day 14.

**0.06 mg BID is the maximum dose in Part 2, but a subject may continue in the study at a lower dose if 0.06 mg BID is not reached by Day 14.

When the 8 subjects in Part 1 have been randomized, and completed 2 weeks of dosing (or discontinued), the sponsor will review all available unblinded safety data for these subjects, including adverse event listings, vital signs, spirometry and ECG data. After receiving feedback from all investigators, and if in the opinion of the sponsor's medical professional there is no evidence of a significant safety finding, dosing in Part 2 will proceed with a 0.06 mg starting dose as described below. If a safety concern is identified by the sponsor's medical physician or by an investigator, or if the sponsor's medical professional believes that the

proposed dosing schedule for Part 2 may not be well-tolerated, the sponsor may decide to adjust the dosing regimen for Part 2, either decreasing the final dose or increasing the interval between up-titrations. There is no plan to pause enrollment between Part 1 and Part 2, but a pause may be implemented if required.

3.1.2 Part 2

Part 2 (Figure 3-2) will consist of approximately 30 subjects who will be randomized in a 2:1 ratio, QCC374 or placebo. The planned dose levels in Part 2 are 0.03 mg and 0.06 mg. Subjects will begin dosing at 0.03 mg bid.

- On Day 7 the investigator will assess an individual subject's clinical status and reported adverse events and confirm that an individual subject can be up-titrated to 0.06 mg bid. This decision, made individually for every subject, will be based on the investigator's assessment of the severity of any adverse events, including adverse events typical of prostacyclins (e.g. headache, jaw pain, myalgia, flushing and nausea).
- On Day 14 the investigator will assess the patient's clinical status and reported adverse events. If the patient is not already receiving the maximum dose of 0.06 mg bid, the investigator will determine whether an individual subject can be up-titrated to 0.06 mg, unless the investigator believes, based on their medical judgement, that the dose should not be increased due to the severity of adverse events. If this dosing scenario occurs, the subject is allowed to continue in the trial, and will continue to receive 0.03 mg bid. This decision, made individually for every subject, will be based on the investigator's assessment of the severity of any adverse events, including adverse events typical of prostacyclins.
- Following the Day 14 visit no further up-titrations are allowed. Subjects are allowed to continue in the trial even if their final dose after titration on Day 14 is not 0.06mg.
- On Day 21, if the subject was up-titrated on Day 14, a follow-up phone call visit will occur to review safety and tolerability.
- At any point during the 16 week treatment period, if the investigator believes, based on their medical judgement, that the dose should be reduced due to the severity of adverse events, the investigator will reduce the dose to the previous tolerated dose. A follow-up phone call should be scheduled 7 days after dose adjustment to review safety and tolerability of adjustment.

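### The protocol gives two starting doses for Part 2, 0.06 mg in Section 3.1.1 and 0.03 mg elsewhere; SAP 1.4 also departs from the protocol on the Part 2 start and maximum

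*Protocol*

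**What the plan says.** **Protocol 3.1.1**, closing text after the Figure 3-2 notes, sets out what follows the review of the first 8 subjects. If the sponsor's medical professional sees no significant safety finding, "dosing in Part 2 will proceed with a 0.06 mg starting dose as described below". If there is a concern, the sponsor may adjust the Part 2 regimen by "either decreasing the final dose or increasing the interval between up-titrations".

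**Protocol 3.1.2**, the description that follows, says: "The planned dose levels in Part 2 are 0.03 mg and 0.06 mg. Subjects will begin dosing at 0.03 mg bid". Day 7 carries a decision on raising the dose to 0.06 mg bid. Day 14 carries a second decision, which opens "If the patient is not already receiving the maximum dose of 0.06 mg bid". A subject not raised on Day 14 stays in the trial and "will continue to receive 0.03 mg bid".

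**Other protocol statements.** The synopsis says that Part 2 "subjects will be randomized in a 2:1 ratio, with a starting dose of 0.03 mg bid". Section 3.1 describes "Part 2, a larger cohort with a 0.03 mg bid starting dose". Section 3.2 records, in the past tense, that 0.03 mg was kept for Part 2 as a result of the Part 1 safety review. The Figure 3-2 notes state that "0.06 mg BID is the maximum dose in Part 2", and also that the Part 2 regimen may change in the light of Part 1.

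**SAP 1.4** gives a planned Part 2 start of 0.06 mg bid and up-titration towards 0.12 mg bid in both parts. Its Figure 1-2 note gives 0.12 mg bid as the maximum without separating the parts, and repeats that the Part 2 regimen may change. SAP 1.2 cites protocol V01.

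**The concern.** The sentence in 3.1.1 does not set out a separate plan. It refers the reader to a description further down, and that description gives a different dose, so the two cannot both be correct as they stand.

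A starting dose is a safety-relevant figure, and Section 3.2 says QCC374 had not previously been tested in PAH patients. The conflict also sits where readers are told to look. Section 6.2 refers to 3.1 and 3.2 for the dosing schedule, Section 6.6 refers to 3.1 for dose adjustments, and the study drug administration row of the Part 2 schedule (Table 8-3) refers to 3.1 and the Site Operations Manual. Section 3.1, with its subsections, contains both values.

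The SAP mismatch matters less. It gives a reader of the SAP the wrong picture of the Part 2 regimen relative to the protocol, but it does not enter any computation.

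**Working it through.** The plan has no statistical figure to reproduce here. The check sets every statement of the Part 2 dose side by side.

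| Place | Part 2 start | Part 2 maximum or target |
|---|---|---|
| Protocol synopsis | 0.03 mg bid | 0.06 mg bid |
| Protocol 3.1 | 0.03 mg bid | not stated |
| Protocol 3.1.1, text after the safety review | 0.06 mg | not stated |
| Protocol Figure 3-2 notes | not stated | 0.06 mg bid |
| Protocol 3.1.2 | 0.03 mg bid | 0.06 mg bid |
| Protocol 3.2 | 0.03 mg | not stated |
| SAP 1.4 and Figure 1-2 note | 0.06 mg bid (planned) | 0.12 mg bid |

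**Size of the discrepancies**

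- Part 2 start, within the protocol: 0.06 / 0.03 = 2.
- Part 2 maximum, SAP against protocol: 0.12 / 0.06 = 2.

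**Does the rest of 3.1.2 fit both starts?** The planned Part 2 levels are 0.03 mg and 0.06 mg, and the maximum is 0.06 mg bid.

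- From 0.03 mg: 0.03 to 0.06 is 1 step, available on Day 7 or, failing that, Day 14.
- From 0.06 mg: the start equals the maximum, so there are 0 steps. The Day 7 and Day 14 decisions would have nothing to decide, and the provision for subjects who stay on 0.03 mg bid after Day 14 would have no subjects to apply to.

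The schedule in 3.1.2 is therefore written around one of the two values and cannot be followed with the other. This shows that the passages are inconsistent. It does not show which dose the sponsor intended, and neither does the number of places giving each value.

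**Does the allowance for change resolve it?** Section 3.1.1 attaches 0.06 mg to the branch with no safety finding. In the other branch it names two adjustments, a lower final dose or a longer interval between up-titrations; a different start is not one of them. Section 3.2 says 0.03 mg was kept as a result of the review. Reading 3.1.1 and 3.2 together, one cannot tell which branch was followed.

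**Does any analysis depend on it?** Protocol 11.1 and SAP Section 4 pool the two parts as QCC374 against placebo. The SAP's first interpretable results already list dose levels 0.03, 0.06 and 0.12, so the dose-level summary accommodates either description.

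**The case against.** The strongest reply is that the order of events settles the matter. The 3.1.1 sentence is a forward-looking rule written before the safety review. Section 3.2 reports the outcome of that review, and 6.2 sends readers to 3.2 as well as 3.1. On this reading the 3.1.1 sentence is simply unrevised text. The Figure 3-2 note also allows the Part 2 regimen to change without limiting what may change, and nothing says the two adjustments named in 3.1.1 are exhaustive. Only 3.1.2 gives a visit-by-visit Part 2 schedule.

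This explains plausibly how the conflict arose, but it is an inference. Nothing in 3.1.1 marks its sentence as superseded, and a general allowance for change does not say which of two stated values is in force.

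A second reply is that no practical harm is shown. That is correct. Packs are blinded (6.1.1), the IRT assigns the first pack (6.3), and 6.1 places the instructions for taking treatment in the Site Operations Manual, which is not among the documents. These controls deliver whichever dose has been set; they do not make the protocol consistent.

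On the SAP, it is fair that 1.4 is descriptive, calls the start planned, and carries its own note that the regimen may change. It is also fair that the documents do not establish that V01 is out of date. The bullet in 3.2 that calls the Part 1 start lower names no comparator and adjoins redacted text, so no error is shown there.

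**Conclusion.** The contradiction is real and lies in the current body text of the protocol: two Part 2 starting doses, 2-fold apart, one of which leaves no room for the up-titration that 3.1.2 schedules. It must be corrected because a starting dose is safety-relevant and the section readers are sent to for dosing contains both values. That judgement rests on the protocol conflict alone and does not assume that anyone was misdosed.

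The SAP discrepancy (planned start 0.06 mg bid, and a maximum of 0.12 mg bid against the protocol's 0.06 mg bid for Part 2) is secondary and leaves the primary comparison unchanged. No position is taken on which dose is right.

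**What to change.** Bring every statement of the Part 2 starting and maximum dose into line with the single regimen the sponsor has adopted. The places are the protocol synopsis, 3.1, 3.1.1, 3.1.2, 3.2 and the Figure 3-2 notes, together with SAP 1.4 and its Figure 1-2 note. At the same time:

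- Confirm that the Day 7 and Day 14 steps in 3.1.2 fit that regimen.
- Check that the 3.2 bullet calling the Part 1 start lower still makes sense beside it.
- If V01 is not the current protocol version, update the version cited in SAP 1.2.

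The cost is low. Protocol 13.1 requires a written amendment with the usual approvals, and the correction can go into the next one. The SAP needs only a text edit. Data collection, analysis sets and models do not change.
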